9.2.2 Adverse Event Overview

An overview of AEs will be presented consisting of the number and percentage of subjects experiencing at least one event for each of the following AE categories:

- Any treatment-emergent AE
- Any COVID-19 related treatment-emergent AE
- Any treatment-emergent AE related to study drug according to the investigator
- Any severe treatment-emergent AE
- Any serious treatment-emergent AE
- Any treatment-emergent AE leading to discontinuation of study drug
- Any treatment-emergent AE leading to death
- AEs of Special Interest
- All deaths
 - COVID-19 related deaths
 - Deaths occurring \leq 84 days after last dose of study drug
 - Deaths occurring $>$ 84 days after last dose of study drug.

COVID-19 cases will be identified using relevant terms for COVID-19 search available in MedDRA version 23.1 or higher. All COVID-19 related AEs and COVID-19 related deaths will be summarized in the TEAE Overview table.

9.2.3 Treatment-Emergent Adverse Events by SOC and/or PT

Treatment-emergent adverse events will be summarized by SOC and PT; by maximum relationship to study drug as assessed by the investigator (e.g., reasonable possibility or no reasonable possibility) and SOC and PT; by maximum severity and SOC and PT; and by

subject number and SOC and PT. Specific adverse events will be counted once for each subject for calculating percentages, unless stated otherwise. In addition, if the same adverse event occurs multiple times within a subject, the highest severity and level of relationship to investigational product will be reported.

In addition, treatment-emergent adverse events will be summarized by PT and sorted by decreasing frequency for the active group.

9.2.4 Treatment-Emergent Adverse Events per Patient-Years of Exposure

Exposure-adjusted AEs per 100 patient-years will be provided, where AEs per 100 patient-years of exposure are defined as the number of AEs divided by the total exposure in 100 patient-years.

9.2.5 SAEs (Including Deaths) and Adverse Events Leading to Study Drug Discontinuation

SAEs (including deaths) and AEs leading to study drug discontinuation will be summarized by SOC and PT and in listing format.

9.2.6 Adverse Events of Special Interest

Adverse events of special interest (AESI) will be summarized by SOC and PT and will be based on standardized or company MedDRA queries (SMQs or CMQs) or based on adjudication results. Adverse events of special interest are categorized as follows:

AESI Grouping	Categories (AESI)	Search Criteria	Terms to Display	Include in AE Overview (Y/N)
Serious Infections and Opportunistic Infections (excluding Tuberculosis and Herpes Zoster)	Serious Infections	Serious PTs of the SOC Infections and Infestations	PTs	Y
	Opportunistic Infections excluding Tuberculosis and Herpes Zoster	Opportunistic infections CMQ excluding Tuberculosis and Herpes Zoster (code 800000189)	PTs	Y
Active Tuberculosis	Active Tuberculosis	Active Tuberculosis CMQ (code 80000188)	PTs	Y
Malignancies	All Possible Malignancies	Narrow Malignancies (SMQ 20000090)	All Possible Malignancies	N
	Malignant Tumours	Narrow Malignant tumours (SMQ 20000194)	Malignant Tumours	Y
	Non-Melanoma Skin Cancer (NMSC)	Broad Skin malignant tumours (SMQ 20000204) excluding terms identified by the Melanoma CMQ (code 80000119)	Non-Melanoma Skin Cancer (NMSC)	Y
	Malignancies excluding NMSC	'Malignancies excluding NMSC' is identified by the 'Malignant Tumours' search excluding terms identified by the 'Non-melanoma skin cancer' (NMSC) search.	PTs	Y

AESI Grouping	Categories (AESI)	Search Criteria	Terms to Display	Include in AE Overview (Y/N)
Hypersensitivity Reaction	Hypersensitivity	Narrow Hypersensitivity (SMQ 20000214)	PTs	Y
Anaphylactic Reaction	Anaphylactic Reaction	Narrow Anaphylactic reaction (SMQ 20000021)	PTs	Y
Hepatic Events	Hepatic Events	Broad Hepatic failure, fibrosis and cirrhosis and other liver damage-related conditions (SMQ 20000013) Broad Hepatitis, non-infectious (SMQ 20000010) Broad Cholestasis and jaundice of hepatic origin (SMQ 20000009) Broad Liver related investigations, signs and symptoms (SMQ 20000008) Narrow Liver-related coagulation and bleeding disturbances (SMQ 20000015)	PTs	Y
Hematologic disorder	Hematologic Events	Broad "Haematopoietic Cytopenias" (SMQ 20000027)	PTs	Y

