#### **Adverse Events of Special Interest**

Below is a list of adverse events of special interest. Related supplemental eCRFs, if applicable, should be filled out in response to an event.

- Serious infections and opportunistic infections
- Active TB (TB screening eCRF in all subjects and supplemental TB eCRF as appropriate)
- Malignancies (all types) (Malignancy eCRF);
- Hepatic events (Hepatic AE eCRF):
  - Discontinuation or interruption of study drug due to a hepatic-related AE;
  - A hepatic-related SAE;
  - ALT/AST > 8 × ULN or ALT/AST > 3 × ULN with a total bilirubin > 2 × ULN;
- Hematologic disorders;
- Hypersensitivity reactions (Hypersensitivity Reaction Signs and Symptom eCRF).

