		ALT or AST $> 8 \times$ ULN	
 
Interrupt study drug dosing and redraw lab with a new sample.
 
If value is confirmed, discontinue study drug and complete supplemental hepatic eCRF.
 

		ALT or AST $> 5 \times$ ULN	
 
Interrupt study drug dosing and redraw lab with a new sample.
 
If value is confirmed for <math>> 2</math> weeks of duration, discontinue study drug and complete supplemental hepatic eCRF.
 

		ALT or AST $> 3 \times$ ULN	
 
Interrupt study drug dosing and redraw lab with a new sample.
 
If value is confirmed and patient has appearance of fatigue, nausea, vomiting, right upper quadrant pain or tenderness, fever, rash, and/or eosinophilia (<math>> 5\%</math>) discontinue study drug and complete supplemental hepatic eCRF.
 
If value is confirmed and total bilirubin <math>> 2 \times</math> ULN or international normalized ratio (INR) <math>> 1.5</math>, discontinue study drug and complete supplemental hepatic eCRF.
 

	Serum Creatinine	$> 1.5 \times$ the baseline value and $>$ ULN	
 
Interrupt study drug dosing and redraw lab with a new sample.
 
If value is confirmed, continue to withhold study drug until value returns to normal reference range or baseline value.
 

		$\geq 2$ mg/dL	
 
Interrupt study drug dosing and redraw lab with a new sample.
 
If value is confirmed, continue to withhold study drug until value returns to normal reference range or baseline value.
 

	ALT or AST	$> 5 \times$ ULN	
 
Interrupt study drug dosing and redraw lab with a new sample.
 
If value is confirmed, send HBV DNA by PCR.
 
If HBV DNA by PCR is positive, discontinue study drug and complete supplemental hepatic eCRF.
 

Subjects who are HBc Ab+ and HBV DNA negative at Screening			

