9.3 Analysis of Laboratory Data

Data collected from central and local laboratories, including additional laboratory testing due to an SAE, will be used in all analyses, except for Baseline where SAE-related laboratory assessments on or before the first dose of study drug will be excluded. The clinical laboratory tests defined in the protocol operations manual (e.g., hematology and clinical chemistry) will be summarized.

Each laboratory variable will be summarized for all time points (starting with Baseline) with the number of non-missing observations, mean and standard deviation, median, minimum and maximum. Mean change from baseline to each applicable post-baseline visit will be summarized for selected laboratory variables, with the number of observations, baseline mean, and visit mean.

The baseline and post-baseline laboratory observations will be categorized as Grade 0, Grade 1, Grade 2, Grade 3, and Grade 4 and shifts from baseline grade to worst on-therapy grade will be summarized. A similar shift table will be provided to summarize shifts from baseline to the final post-baseline value. Toxicity grading scale is based on CTCAE version 4.03 ([Appendix B](#)).

Laboratory abnormalities will be evaluated based on Potentially Clinically Significant (PCS) criteria ([Appendix B](#)). For each laboratory PCS criterion, the number and percentage of subjects who have a laboratory value meeting the criteria will be summarized. Listings will be provided to summarize subject-level laboratory data for subjects meeting PCS criteria.

In addition, ALT/SGPT, AST/SGOT, alkaline phosphatase, and total bilirubin will be categorized as follows:

- ALT $\geq 3 \times$ ULN
- ALT $\geq 5 \times$ ULN
- ALT $\geq 10 \times$ ULN
- ALT $\geq 20 \times$ ULN

- $\text{AST} \geq 3 \times \text{ULN}$
- $\text{AST} \geq 5 \times \text{ULN}$
- $\text{AST} \geq 10 \times \text{ULN}$
- $\text{AST} \geq 20 \times \text{ULN}$
- $\text{TBL} \geq 2 \times \text{ULN}$
- $\text{Alkaline phosphatase} \geq 1.5 \times \text{ULN}$
- $(\text{ALT and/or AST} \geq 3 \times \text{ULN}) \text{ and } (\text{TBL} \geq 1.5 \times \text{ULN})$
- $(\text{ALT and/or AST} \geq 3 \times \text{ULN}) \text{ and } (\text{TBL} \geq 2 \times \text{ULN})$

where ULN is the upper limit of normal.

A listing of potentially clinically significant liver function laboratory values will be provided. The listing will include all subjects who met any of the following 4 criteria:

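### The SAP's Hepatic Events AESI is a MedDRA-query count that does not implement the protocol's hepatic AESI criteria, and the difference is not recorded

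*SAP*

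**What the plan says.** Protocol 6.1 (Adverse Events of Special Interest) opens with "Below is a list of adverse events of special interest" and includes hepatic events, tied to the Hepatic AE eCRF. Three bullets beneath that item say what qualifies:

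- The first turns on what was done with the drug: "Discontinuation or interruption of study drug due to a hepatic-related AE".
- The second turns on seriousness: any SAE that is related to the liver.
- The third turns on laboratory values: "ALT/AST > 8 × ULN or ALT/AST > 3 × ULN with a total bilirubin > 2 × ULN".

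The last bullet holds two laboratory criteria, so there are four in all. The 8 × ULN level is also a threshold in Protocol Table 2.

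SAP 9.2.6 states that AESI summaries "will be based on standardized or company MedDRA queries (SMQs or CMQs) or based on adjudication results". Its Hepatic Events row names five SMQs: four in broad scope (one of them the query on liver investigations, signs and symptoms) and one in narrow scope. The row contains no seriousness, drug-action or laboratory condition, and it is marked for inclusion in the AE overview.

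SAP 9.3 introduces its liver categories with "In addition, ALT/SGPT, AST/SGOT, alkaline phosphatase, and total bilirubin will be categorized as follows". The cuts for ALT and for AST are 3, 5, 10 and 20 × ULN. The section also tabulates ALT and/or AST ≥ 3 × ULN with bilirubin ≥ 2 × ULN, and it provides liver listings.

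SAP 1.0 says that changes to protocol analyses are outlined in Section 13.0. The version history there mentions nothing about hepatic AESIs.

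**The concern.** Protocol and SAP use the same name for two different quantities. Someone who reads the overview line for hepatic AESIs with the protocol in hand will assume that each subject counted met one of the protocol's criteria. Under the SAP as written, a subject is counted because an AE term falls in one of the queries, however mild the event, and the protocol's qualifiers play no part.

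Protocol 2.2 says that Phase 1 did not suggest a potential for drug-induced liver injury, but it still asks for timely detection and follow-up of suspected cases in this study. The hepatic AESI is the protocol's own definition of which liver events deserve special attention. With about 40 subjects, one subject moves a percentage by 1/40 = 2.5 points, so it matters which definition a subject met.

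**Working it through.** No sample size, power or error rate is involved, and the plan states no figure to reproduce. The check is to take each protocol criterion and look for the SAP output that would report it.

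| Protocol 6.1 criterion | SAP output | Result |
|---|---|---|
| Discontinuation for a hepatic AE | 9.2.5: all AEs leading to discontinuation, by SOC and PT, with listings | Can be found, but not as a hepatic AESI count |
| Interruption for a hepatic AE | None; 9.2.2 and 9.2.5 cover discontinuation only | Not identified in any output |
| Hepatic SAE | 9.2.5: all SAEs, by SOC and PT, with listings | Can be found, but not as a hepatic AESI count |
| ALT/AST > 8 × ULN | 9.3 cuts at 3, 5, 10 and 20; Appendix B Grade 3 is > 5 to 20 × ULN; Appendix C cut is > 5 × ULN | No summary count; in listings only |
| ALT/AST > 3 × ULN with bilirubin > 2 × ULN | 9.3: ≥ 3 with ≥ 2 × ULN tabulated; possible Hy's Law cases listed | Reported, with ≥ in place of > in the table |
| Any of the above | None | Composite not assembled |

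**How far the tables pin down the 8 × ULN count.** The SAP categories are cumulative. For ALT alone, N(≥ 10) ≤ N(> 8) ≤ N(≥ 5), and likewise for AST. If no subject reaches 5 × ULN, the count above 8 × ULN is known to be zero. Otherwise a subject with a peak above 8 but below 10 × ULN falls in the same rows (≥ 3 and ≥ 5) as one with a peak of exactly 5 × ULN. The protocol criterion also takes either enzyme, whereas the SAP's single-enzyme rows are separate. The number of subjects with either enzyme above 8 × ULN is therefore bounded only by

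max{N_ALT(≥ 10), N_AST(≥ 10)} ≤ N ≤ N_ALT(≥ 5) + N_AST(≥ 5).

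**What the listings add.** SAP 9.3 lists every subject with ALT or AST ≥ 3 × ULN. It also gives subject-level listings for anyone meeting the potentially clinically significant criteria, which for ALT and AST means > 5 × ULN. Since 8 > 5 > 3, everyone above 8 × ULN is in the first, and in the second too provided the value is more extreme than that subject's baseline, as Appendix C requires.

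**Could the SAP do otherwise?** The same AESI table applies a seriousness condition to infections, so a protocol qualifier can be carried into it. The SAP sentence also allows adjudication results, but the hepatic row names none, and neither document describes hepatic adjudication.

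**The case against.** Five points on the other side deserve weight.

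- **Most of the information is reported somewhere.** A reader might infer from the mismatch that the protocol's hepatic AESI is never counted. The documents do not support that. The criterion with bilirubin is tabulated and listed, and hepatic SAEs and discontinuations appear in SAP 9.2.5. This stands, and it limits the point to the missing composite, the missing 8 × ULN count and the missing interruption output.
- **Subjects above 8 × ULN can be found.** A reader might also infer that a peak between 8 and 10 × ULN cannot be told apart from one at 5 × ULN. That is true of the tables but not of the listings, provided these print the values. With about 40 subjects, reading them is feasible.
- **A value above 8 × ULN is unlikely to go unrecorded.** The protocol's AE definition includes abnormal laboratory findings, 6.1 names the criterion, and Table 2 ties a confirmed value to the hepatic eCRF. A qualifying value missing from the AE data is possible, but nothing suggests it should be expected.
- **The bullets may only be eCRF triggers.** They follow an instruction about supplemental eCRFs, and Protocol 7.4 leaves safety analysis detail to the SAP. The reading is possible, but the sentence above the bullets presents them as the AESI list. Even if the reading were right, the shared label would still need explaining.
- **Broad queries are a defensible choice for sensitivity.** The row displays preferred terms, and SAP 9.2.3 summarises events by maximum severity. This stands as a reason to keep the SMQ line. How many minor events the queries would admit depends on term lists that are not in the documents, so no amount of dilution can be claimed.

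**Conclusion.** The SAP's Hepatic Events AESI does not implement the protocol's hepatic AESI, and Section 13.0 does not say so. Followed as written, the plan puts a query-based count in the AE overview, never assembles the protocol composite, gives no summary count for ALT/AST above 8 × ULN, and does not identify hepatic AEs that led to interruption of study drug.

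The severity is minor. Only safety reporting is affected; no efficacy analysis depends on it. The documents give no hepatic event rates, so the difference between the two counts cannot be estimated, and the 2.5 points per subject describes the study's size rather than the error.

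The conclusion rests on two assumptions: that the bullets in Protocol 6.1 define the AESI, as their introductory sentence indicates, and that the liver listings show the values themselves. If the listings do not show values, the gap at 8 × ULN is wider than stated here.

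**What to change.** In SAP 9.2.6, add a derived subject-level flag and an overview row for the protocol 6.1 hepatic AESI: a hepatic SAE, a hepatic AE leading to interruption or discontinuation, ALT/AST > 8 × ULN, or ALT/AST > 3 × ULN with bilirubin > 2 × ULN. Show the components beneath the total. State which AEs count as hepatic (the existing SMQ search could serve) and whether the transaminase and bilirubin values must come from the same sample, which Protocol 6.1 does not say.

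Keep the SMQ count as a separate line with a label that shows it is query-based. Add ALT > 8 × ULN and AST > 8 × ULN to the SAP 9.3 categories.

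If the sponsor intends the SMQ definition to replace the protocol's, the two passages should be reconciled and the change entered in Section 13.0.

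The cost is one derived flag, one overview row with its components, and two laboratory rows. The inputs are laboratory values, AE data and the hepatic eCRF, all of which are already planned. No clinical rule changes.

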### 2.2 Benefits and Risks to Subjects

---

Despite the availability of various UC therapies, including biologic and small molecule therapies, many patients still do not respond adequately to these treatments, gradually lose response over time or discontinue treatment due to significant adverse events (AEs). Thus, there remains a large unmet medical need for additional therapeutic options in UC for patients with inadequate response or intolerance to available therapies. Based on pre-clinical, clinical, and translational evidence, ravagalimab could potentially demonstrate efficacy with a favorable safety profile in the treatment of patients with moderately to severely active UC who have failed or have intolerance to approved biologics and/or tofacitinib.

In the Phase 1 studies ravagalimab was safe and well tolerated with no serious or severe AEs observed in healthy adult subjects. The dose regimen in Study M15-722 will not exceed the doses evaluated in the Phase 1 studies.

As with any immune modulating agent, ravagalimab has the potential to impair immune function resulting in a potential risk of infection, including opportunistic infections. The role of ravagalimab in tumor immunity is not well established at this time, but an increased risk of cancer associated with ravagalimab treatment cannot be excluded. Though the completed Phase 1 studies did not suggest a potential for drug-induced liver injury (DILI) with ravagalimab, DILI is under constant surveillance by sponsors and regulators and any suspected event of DILI in this study requires timely detection, evaluation, and follow-up of laboratory parameters. Local reactions to intravenous (IV) infusions or subcutaneous (SC) administered biologic therapies are uncommon, and are usually limited to redness, swelling, or induration at injection site. In Phase 1 studies, 1 subject on ravagalimab each experienced injection site reaction and injection site pain. The aforementioned safety risks were taken into account with the establishment of the safety monitoring measures in the eligibility criteria for this study. Furthermore, an internal data monitoring committee (DMC) will monitor safety at regular intervals (Section 6.3).

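### The SAP takes herpes zoster out of the opportunistic-infection AESI query and gives it no row of its own, so non-serious zoster is counted in no AESI category

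*SAP*

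**What the plan says.** **Protocol.** Section 6.1, under Adverse Events of Special Interest, lists "Serious infections and opportunistic infections" with no exception, and active tuberculosis as a separate item. Section 2.2 says that the drug has the "potential to impair immune function resulting in a potential risk of infection, including opportunistic infections". Neither passage mentions herpes zoster, and the protocol does not define which infections count as opportunistic.

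**SAP.** Section 9.2.6 turns the protocol list into a table of groupings, categories and search criteria. The first grouping is headed "Serious Infections and Opportunistic Infections (excluding Tuberculosis and Herpes Zoster" and has two categories:

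- Serious Infections, searched as "Serious PTs of the SOC Infections and Infestations".
- Opportunistic infections, searched as "Opportunistic infections CMQ excluding Tuberculosis and Herpes Zoster (code 800000189".

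The next grouping restores tuberculosis through "Active Tuberculosis CMQ (code 80000188". No grouping or category restores herpes zoster. Section 9.2.2 makes AESIs one of the categories in the adverse event overview. Outside the AESI table, Section 9.2.3 says: "Treatment-emergent adverse events will be summarized by SOC and PT".

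**The concern.** An exclusion from a composite safety query is normal when the excluded item is reported separately, and tuberculosis is handled that way. For herpes zoster only the first half is done. It is removed from the query and put nowhere else, and neither document gives a reason.

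Infection, including opportunistic infection, is the first drug risk that Protocol 2.2 names. Subjects may also stay on oral corticosteroids and on azathioprine, mercaptopurine or methotrexate (Protocol 5.1 and 5.4). The AESI block is where a reader of the study report looks first for that risk. If the search rule is programmed as written, an AESI infection count can be complete by its own definition and still omit every non-serious zoster case.

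**Working it through.** There is no power, alpha or event-count figure to reproduce. The check is a row-by-row reading of the SAP 9.2.6 table, asking which search criterion could return a zoster event.

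| Category in SAP 9.2.6 | Serious zoster | Non-serious zoster |
|---|---|---|
| Serious Infections | Yes, by its search criterion | No, limited to serious events |
| Opportunistic Infections | No, excluded by name | No, excluded by name |
| Active Tuberculosis | No | No |
| Malignancy (4 categories) | No | No |
| Hypersensitivity | No | No |
| Anaphylactic Reaction | No | No |
| Hepatic Events | No | No |
| Hematologic Events | No | No |

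**Count.** 1 + 1 + 1 + 4 + 1 + 1 + 1 + 1 = 11 categories. One can capture serious zoster, and none is designed to capture non-serious zoster. Of the two infections excluded from the opportunistic-infection query, one (tuberculosis) has a replacement row and one (zoster) has none. The entries for the non-infection queries are inferred from their subject matter, because their term lists are not in the documents.

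**Heading against row.** The exclusion appears in the grouping heading, which stands above both infection categories, and again in the opportunistic-infection category and its search. It does not appear in the Serious Infections search. The row-level criterion keeps serious zoster, but a programmer who applied the heading to the whole grouping would drop it.

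**Where non-serious zoster still appears.** SAP 9.2.3 plans treatment-emergent events by system organ class and preferred term, by maximum relationship, by maximum severity, by subject number, and by preferred term in order of frequency. SAP 9.1 and 9.2.4 plan exposure-adjusted rates. In the overview (SAP 9.2.2) such a case counts under any treatment-emergent event and, where it applies, under related, severe or leading to discontinuation. It is absent only from the AESI lines.

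**Illustration of size.** Neither document gives a zoster rate. Assume 1 to 3 non-serious cases among 40 subjects: 1/40 = 2.5% and 3/40 = 7.5%. The AESI tables would show 0 of these cases, and the general tables would show all of them.

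**Clerical check.** The opportunistic-infection code is printed as 800000189, which has nine digits. The other two company-query codes in the table, 80000188 (active tuberculosis) and 80000119 (melanoma), have eight. This says nothing about zoster coverage, but the search key should be verified before programming.

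**The case against.** The strongest reply is that the SAP does not contradict the protocol. The protocol never names zoster and does not define opportunistic infection, and its Section 7.4 leaves the details of each safety analysis to the SAP. On that view, whether ordinary non-serious zoster belongs among the AESIs is the sponsor's choice. The exclusion is also printed openly in the heading, the category and the search, so a reader of the table is told that zoster is not counted there. SAP 9.2.6 further allows AESIs to be based on adjudication results.

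Most of this stands. It rules out calling the omission a breach of the protocol. It does not explain why one of two excluded infections is restored and the other is not, and neither document describes an adjudication process for zoster. Visibility in the general tables is not a full answer either: it holds for tuberculosis too, which was still given a row.

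A reader might infer more than the documents support:

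- **That zoster is hidden from safety reporting, or survives only as an isolated line.** It does not: several general tables, a by-subject summary and the exposure-adjusted rates all include it.
- **That disseminated or multidermatomal zoster that is not serious is also lost.** The query's term list is not in the documents, so which zoster terms it removes cannot be seen.
- **That the SAP failed to declare a change from the protocol in its Section 13.** That would first require the protocol to count zoster as opportunistic, which it does not say. The Section 13 table summarises changes between SAP versions, and the earlier versions are not available for comparison.

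**Conclusion.** The point holds as a gap in the AESI definition. Followed as written, SAP 9.2.6 captures non-serious herpes zoster in none of its 11 categories and in no AESI line of the overview. Serious zoster is still captured under Serious Infections, provided the grouping heading is not read as overriding that row's criterion.

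The consequence is limited to the AESI summaries. Data collection, the general adverse event tables and the exposure-adjusted rates are unaffected. The conclusion rests on two assumptions: that the company query removes zoster as its label says, and that no unstated adjudication step puts it back. The range of 1 to 3 cases in 40 only illustrates the effect and is not evidence of harm. The change is still worth making before programming, because the count is incomplete for a risk that the protocol itself puts first.

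**What to change.** 1. Add a Herpes Zoster row to the SAP 9.2.6 table beside Active Tuberculosis, with a zoster query or a list of preferred terms as the search, preferred terms displayed, and inclusion in the adverse event overview set to Y.
2. State that the exclusion in the grouping heading applies to the opportunistic-infection category only, and that serious zoster stays in Serious Infections.
3. Verify code 800000189 against the query library and correct it if it is a typing error.

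A separate row is better than deleting zoster from the exclusion. Deletion would label zoster as opportunistic, which the protocol does not say, and would need a different query from the one cited. If the sponsor intends zoster not to be an AESI, one sentence giving the reason is the minimum.

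The cost is one more query and one more table row. No new data are collected.
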